Finally, to specify possible mechanisms of action to promote a behavior, such techniques and functions must be connected to influences on behavior following this model. The proposed mechanisms of action to facilitate adherence behavior in WelTel were: a) the delivery of an external trigger (SMS reminder to complete a behavior) and social support, to influence opportunities and automatic motivation through restructuring and environmental clearance; b) delivery of health-related information and social support to influence ability, opportunity, and motivation through education, persuasion, and training. We believe that retention in HIV care will be similarly influenced in our intervention.

General description:

This intervention will be designed for MSM who are HIV positive. We will recruit subjects 18 years of age or older. The intervention will begin one day after enrollment. The two-way SMS intervention will have four components: 1) an automated weekly SMS sent to ask how they are doing (basic follow-up); 2) phone calls from a health provider to participants who respond that they have a problem, or that they need support or some information that cannot be resolved by text message; 3) SMS reminder 1 week before an appointment for HIV care.

Design:

Randomized controlled trial.

Main result:

The primary outcome will be retention in HIV care for up to 1 year after enrollment. Participants will be classified as retained in care if they attend three HIV care appointments that are separated by 90 days or more within a one-year period (at the study HIV center) (64). Otherwise, they will be classified as not retained. The delivery of the intervention will last 6 months and the follow-up period to verify retention will last up to 12 months.

Main exposure:

Text message (SMS) based intervention delivered through the WelTel system by trained health providers.

Procedures:

- 1. **Recruitment and eligibility criteria**. We will identify and recruit 208 HIV+ MSM in the Cayetano Heredia Hospital HIV service for a period of up to 12 months. Eligible participants will be 1) men who have sex with men; 2) 18 years or older; 3) has been diagnosed HIV positive; 4) own a cell phone that can send and receive SMS; 5) resides in Lima; and 6) not be enrolled in another study that uses text messaging.

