- 2. Enrollment and randomization: During enrollment, the recruiter will be blinded to assignment to the intervention group. The recruiter will obtain informed consent and instruct the participant on how he should interact if he starts receiving text messages (see appendix 1). Participants will be randomly assigned after providing their cell phone number and brief general information (first name, date of diagnosis, email). They will be assigned a study ID and randomly divided into intervention or control arm (1:1 ratio) using computer generated random numbers. Arm assignments will be in sequentially numbered sealed envelopes. Healthcare providers trained to administer the intervention will be informed by the research team when a new participant is enrolled in the intervention arm. Due to the nature of the study, healthcare providers and participants will not be blinded to group assignment. The participants assigned to the intervention arm will have their telephone numbers registered on the platform.
- 3. Intervention. We will use the WelTel platform. For 6 months, every Monday the system will send automatic SMS with the question "How are you?" or similar questions (How are you?; How are you doing?). Participants will be instructed to respond if they are okay ("All OK") or if they have a problem ("I want support"; "I'm not okay"). The provider will send a return SMS to participants who have a problem or query; or they will call those who need it. The WelTel program has a customizable dictionary that identifies the words (or phrases) that the administrator indicates; thus, the answers of the participants are automatically ordered to indicate who needs follow-up through a reply SMS or call. One week before each appointment for HIV care, health providers will send an SMS reminder (Table 1).

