- 4. Standard care arm. In 2018, the government published new national guidelines for HIV care (65). After pre-test counseling, the diagnosis of HIV is made with two rapid tests. Those who test positive for both tests receive post-test counselling, including emotional support, and are linked to an ART initiation center, ideally within the same week. During the first medical appointment after diagnosis, laboratory tests including CD4 and viral load (VL) are requested. In most cases, initiation of antiretroviral treatment (ART) occurs at the second medical appointment when basic laboratory results are available. Currently, it is not mandatory to have CD4/CV results available to start ART. ART, viral load and CD4

lab tests are provided free of charge. It is recommended that patients have CD4 counts and viral load testing twice during the first year. A one-month supply of ART is initially provided. If patients are adherent, nurses dispense ART every 3 months and also assess adherence.

Table 1. Summary of the study: exposures, results and design.

Component	Sub-	Description						
	component							
	Basic follow-up	Weekly automatic SMS with the question "How are you?" or similar						
	SMS (check-in)	messages. This will be shipped for 6 months.						
Intervention	Calls	The provider can call participants who have a problem.						
arm	Appointment	SMS reminder one week before each appointment for HIV care.						
(exposure)	reminders							
	Primary	Retention in HIV care up to 1 year after enrollment, defined as attending 3						
Results		appointments that are 90 days apart within a 1-year period.						
	Desing	Randomized controlled trial with a parallel group.						
		We aim to increase retention in HIV care from 50% to 70%. With 104						
	Sample size	participants in each arm, we will have 80% power to detect this difference						
Design	Follow-up	6 months (intervention); 12 months (retention measure).						
	Theory	The behavior change wheel framework and its model of Capability,						
		Opportunity, Motivation and Behavior.						
	Standard of care	Post-test counselling, including emotional support and linkage to ART						
Control arm		initiation, ideally within a week. ART, CD4, and viral load laboratory tests are						
		provided free of charge in Peru.						

Analysis plan:

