 Data sources for the main result. The main outcome to be measured will be retention in HIV care during the first year after enrollment. Retention in care will be considered if they attend 3 HIV care appointments that are at least 90 days apart within a one-year period (64). We will verify retention in HIV care with: study registration (enrollment) sheets, physical medical records from the HIV service, reception appointment notebooks, and with a final follow-up survey.

Health providers will enter the data from the enrollment registration sheets into a database that will be stored in a password-protected computer file. The data from the final follow-up online survey completed by the participants will be exported to the physical database and will be periodically deleted from the online survey system server. All data resulting from the interaction between providers and participants will be stored on the WelTel platform that has high security standards: encrypted, password protected and HIPAA compliant (*The Health Insurance Portability and Accountability Act*).

Statistic analysis. for the main outcome, we will compare the proportion of MSM who
were retained in care in both groups, as a cumulative incidence rate. If any variable of
interest is not balanced between intervention and control arms, we will calculate Mantel

Haenszel-adjusted relative risks (RR). For secondary outcomes, we will also assess differences in the proportion of participants.

3. **Calculation of the sample size**. We hope to increase retention in HIV care from 50% to 70% one year after enrollment in the study clinic among HIV+ MSM. With 104 participants in each arm, we will have 80% power to detect this difference.

Our main outcome is the degree of loss to follow-up. Retention in care at the study HIV service (as opposed to being lost to follow-up) is the primary outcome, and retention in any HIV clinic will be a secondary measure. Participants lost to follow-up will be considered as not retained. We will measure the retention in an establishment of the Ministry of Health (MINSA). MINSA provides care to more than 60% of Peruvians (73). Since retaining subjects in our public health system is an important goal, we have not adjusted the sample size calculation based on the potential loss of subjects to follow-up.

OPERATIONALIZATION OF VARIABLES

Table 2. Operationalization of variables.

Variable	Туре	Options	Source				
Age	Continuous	> 18	Online follow-up survey				

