Education	Categorical	Secondary, Technical, Superior,	Online follow-up survey				
Civil status	Categorical	Single, Married, Outgoing, Coupled	Online follow-up survey				
Employment situation Categorical		Unemployed, Employed	Online follow-up survey				
Nationality	Categorical	Peruvian, Foreign	Online follow-up survey				
sexual orientation	Categorical	Gay, Bisexual, Straight	Online follow-up survey				
Diagnosis date	Date	Day month Year	Clinic history; dating record				
Treatment start date	Date	Day month Year	Clinic history; dating record				
Attended appointment dates	Date	Day month Year	Clinic history; dating record				
Viral load	Continuous		Clinic history				
CD4	Continuous		Clinic history				
alcohol use	numeric		Online follow-up survey				
Condom use, last encounter	Categorical	Yes, No	Online follow-up survey				
Email	Text		enrollment sheet				
Cell phone number	Numeric	NA	enrollment sheet				
Arm	Categorical	Control, Intervention	Study Database				
Retention in HIV care	Categorical	If not; Attend three appointments for HIV care that are 90 days or more apart within a one-year period (at the study HIV center)	Clinic history; dating record; online follow-up survey; WelTel system				

TIMELINE

Actividades		Year 1			Year 2			Year 3			Year 4					
	1	2	3	4	1	2	3	4	1	2	3	4	1	2	3	4
Recruitment/Enrollment																
Delivery of intervention																
Monitoring and analysis																
Manuscript development																

REFERENCES

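### Table 2 names the WelTel platform, on which only intervention-arm men are registered, as a source for primary retention; the main-result source list and Table 2's visit-date row do not (minor)

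*Combined protocol and SAP*

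**What the plan says.** The document describes the sources of primary retention in three places.

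- Operationalization of variables, Table 2, retention row: "Clinic history; dating record; online follow-up survey; WelTel system". This row carries the primary definition, tied to the study HIV center, so it is not the secondary any-clinic measure.
- Analysis plan, data sources for the main result: "We will verify retention in HIV care with: study registration (enrollment) sheets, physical medical records from the HIV service, reception appointment notebooks", followed by a final follow-up survey. WelTel is not listed as a source. The same section mentions it only for storage: "All data resulting from the interaction between providers and participants will be stored on the WelTel platform".
- Table 2, row "Attended appointment dates": the source column gives clinic history and dating record only.

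Three other statements bear on the point.

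- Procedures, item 2 (enrollment and randomization): "The participants assigned to the intervention arm will have their telephone numbers registered on the platform". Nothing in the document places control participants on it.
- Main result, on men who do not meet the three-visit rule: "Otherwise, they will be classified as not retained".
- On timing, General description says "The intervention will begin one day after enrollment", and Main result gives 6 months of delivery within 12 months of outcome follow-up. Table 1 describes the appointment message as "SMS reminder one week before each appointment for HIV care".

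**The concern.** Most mismatches between source lists are harmless because the source in question exists for everyone. This one affects one arm only. If the Table 2 retention row is followed, the person classifying outcomes has a further record to consult for an intervention man and none for a control.

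The outcome rule gives the asymmetry a direction. A man is not retained unless three suitably spaced visits are shown, and men lost to follow-up also count as not retained. An extra source used to add visits can therefore only move men from not retained to retained, and only in the intervention arm. This holds even if the added visit really took place, because a control's unrecorded visit has no equivalent second chance.

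Providers and participants are unblinded, and the document gives no rule for resolving sources that disagree. At stake is whether the primary outcome is ascertained in the same way in both arms.

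**Working it through.** **The source lists side by side**

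| Source | Analysis plan, main result | Table 2, retention | Table 2, attended dates |
|---|---|---|---|
| Enrollment sheets | yes | no | no |
| Clinic records | yes | yes | yes |
| Appointment notebooks / dating record | yes | yes | yes |
| Follow-up survey | yes | yes | no |
| WelTel | no | yes | no |

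WelTel is the only entry that the document ties to one arm.

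**How far WelTel could reach**

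If the three visits are each at least 90 days after the one before, and the first falls at or after enrollment, the third falls on day 2 × 90 = 180 or later. Delivery runs from day 1 to about day 365.25 / 2 = 183. On that reading WelTel could bear almost only on the first two visits. A reminder sent a week ahead shows that a visit was scheduled, not that it was attended.

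**The plan's own figure**

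The plan states 104 per arm for 50% against 70% with 80% power. It states no alpha; two-sided 5% is assumed here.

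n₀ = [1.96·√(2·0.6·0.4) + 0.8416·√(0.5·0.5 + 0.7·0.3)]² / 0.2² = 93.0

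With continuity correction: n = (n₀/4)·[1 + √(1 + 4/(n₀·0.2))]² = 102.8, so 103.

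The stated 104 is reproduced to within one, and only with the correction. Nothing in this point changes it.

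**Illustration of size**

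Inputs from the plan: 104 per arm and 50% retained. Assumptions not in the plan: no true effect, the test, alpha, and the share f of non-retained intervention men whom WelTel alone would reclassify.

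- Expected non-retained men per arm: 104 × 0.50 = 52.
- Apparent intervention retention: 0.50 + 0.50·f.
- Test statistic: z = |p̂₁ − p̂₀| / √(2·p̄(1 − p̄)/104). The corrected version subtracts 1/104 from the numerator.
- Rejection probability: the sum, over all pairs of counts with z > 1.96, of the product of the two binomial probabilities.

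| f | Men (of 52) | Apparent retention | RR | Uncorrected: two-sided / favouring intervention | Corrected: two-sided / favouring intervention |
|---|---|---|---|---|---|
| 0 | 0 | 50% vs 50% | 1.00 | 4.5% / 2.2% | 3.2% / 1.6% |
| 2% | 1.04 | 51% vs 50% | 1.02 | 4.7% / 3.1% | 3.4% / 2.3% |
| 5% | 2.6 | 52.5% vs 50% | 1.05 | 5.9% / 5.0% | 4.4% / 3.7% |

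With 1, 2 or 3 whole men reclassified, the two-sided rate is 4.7%, 5.3% or 6.4% uncorrected, and 3.4%, 3.9% or 4.7% corrected. With 45% or 55% retained and f = 5%, it is 6.3% or 6.1% uncorrected, and 4.7% or 4.5% corrected.

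**The case against.** The strongest reply is that the pathway is nearly closed by the plan itself. Retention is computed from visit dates, and the Table 2 row for those dates takes them only from clinic history and the dating record. No section describes WelTel recording attendance; it holds message exchanges, and its reminders precede the visit. The section devoted to the main result omits WelTel altogether. To be reclassified, a man would need clinic records that show the late visit but miss an earlier one that a WelTel exchange happens to mention. Nothing links 2% or 5% of non-retained men to that narrow group.

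This stands as far as weight is concerned. It does not remove the mismatch: the retention row still names WelTel, and no sentence bars its use.

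A second reply also stands. Whether the two-sided error exceeds 5% depends on an assumed test. With the continuity-corrected test, every scenario listed above stays below 5%. The rate favouring the intervention still rises under both tests.

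A reader might infer that WelTel logs visits, or that reminders would be counted as visits, and so that the primary result will be biased. The documents support neither inference.

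**Conclusion.** The inconsistency is real and one-sided, but minor. Following the Table 2 retention row gives the intervention arm alone an additional source for an outcome that defaults to not retained. Following the Analysis plan's list does not.

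The direction is conditional: if WelTel were used to add visits, the error could only favour the intervention. The size cannot be derived, because the documents give no reclassification share and do not say what WelTel would contribute. It is probably small. At an assumed 5% share, the apparent difference is 2.5 percentage points against the planned 20.

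It would go too far to say that the trial's false-positive rate exceeds 5%. The documents state neither the test nor alpha, and the same assumed share gives 5.9% with one common test and 4.4% with another. What is established is a risk of unequal ascertainment, not a demonstrated bias.

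**What to change.** Delete the WelTel entry from the source column of the Table 2 retention row. Add to the Analysis plan, under data sources for the main result: *Primary retention is classified only from sources available in the same way in both arms; WelTel data are not used to classify it.* Do this before data extraction, so that the choice is not made with the outcomes in view.

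The cost is two words removed and one sentence added, with no new data, staff, visits or change in sample size. The downside is that a visit evidenced only in WelTel is not counted.

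The survey, which both lists name, can stay as planned. The plan says that participants complete it; that this means both arms is an inference, which the new sentence turns into a condition. After this change the two lists still differ on the enrollment sheets. Nothing ties those to one arm, so that is a matter of tidiness only.
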